	June 23, 2022	
to patients who were not receiving dialysis when they entered the trial and not on dialysis at the time of transplant. Time Frame: 4.1 Years
 
Added Clarification:
 
 1. A potential living kidney donor begins their evaluation at a transplant centre to donate a kidney to the patient and/or a patient receives a living donor transplant. Description: Given that the average wait time for a deceased donor kidney transplant is five years on average in Ontario, our intervention is likely to have only a small impact on the rate of deceased donor kidney transplants. For this reason, we have pre-specified five secondary outcomes to examine the impact of our intervention on living kidney donor transplant activity. Time Frame: 4.17 Years 2. Time to first occurrence of a potential living kidney donor beginning their evaluation at a transplant centre to donate a kidney to the patient. Description: Secondary outcome selected to understand living kidney donor transplant activity. Time Frame: 4.17 Years 3. A transplant centre receives a patient's complete referral package from a chronic kidney disease program and at least one potential living kidney donor begins their evaluation at a transplant centre to donate a kidney to the patient. Description: Secondary outcome selected to understand living kidney donor transplant activity. Time Frame: 4.17 Years 4. A patient receives a living donor kidney transplant. Description: Secondary outcome selected to understand living kidney donor transplant activity. Time Frame: 4.17 Years 	
All secondary outcomes were listed in our original published protocol. No secondary outcomes were changed. We now provide additional details as we thought that the interpretation could be subjective. Please refer to our published statistical analysis plan for further details. No change was made to the time frame. We simply are providing a more precise time frame and this precise time frame aligns exactly with our published statistical analysis plan.

Revision	Date of Revision	Details of Revision	Rationale
		
5. Pre-emptive living donor kidney transplants (restricted to patients who were not receiving dialysis when they entered the trial and not on dialysis at the time of transplant).
 
Description: Secondary outcome selected to understand living kidney donor transplant activity.
 
Time Frame: 4.17 Years
	
Other pre-specified outcomes	August 7, 2020	
Added: We will consider several other outcomes in an exploratory analysis. Other outcome measures, include:
 
 1. Rate of deceased donor kidney transplant Description: Rate of deceased donor kidney transplant censoring at death and receipt of a living donor kidney transplant. Time Frame: 4.1 Years 2. Average number of months from the date of dialysis initiation (i.e. trial entry) to the date of referral. Description: This outcome is assessed in patients receiving maintenance dialysis who were referred to a transplant centre. Time Frame: 4.1 Years 3. Rate of living kidney donor transplants Description: This outcome is assessed in patients waitlisted for a deceased donor kidney transplant and censored at death and receipt of a deceased donor kidney transplant. Time Frame: 4.1 Years 4. Proportion of pre-emptive transplants Description: This outcome is assessed in recipients of a living kidney donor transplant and restricted to patients who were not receiving dialysis when they entered the trial and not on dialysis at the time of transplant. Time Frame: 4.1 Years 5. Average number of months from the date of referral to a transplant centre to the date the first living donor candidate contacts the transplant centre for the intended recipient Description: This outcome is assessed in recipients of a living kidney donor transplant. 	All other outcomes provide additional important information about access to kidney transplant. Further details on these measures can be found in our published trial protocol.

Revision	Date of Revision	Details of Revision	Rationale
	June 23, 2022	
Time Frame: 4.1 Years
 
6. Average number of months from the date of referral to a transplant centre to date of the transplant surgery Description: This outcome is assessed in recipients of a living or deceased donor kidney transplant.
 
Time Frame: 4.1 Years
 
Added Clarification:
 
 1. Rate of deceased donor kidney transplant Description: Rate of deceased donor kidney transplant censoring at receipt of a living donor kidney transplant and at the censoring events included in the main trial analysis (i.e., emigration, trial end date [December 31, 2021], death, evidence of recovered kidney function, or on the date a recorded contraindication to transplant occurs [with the exception of age >75]). 3. Rate of living kidney donor transplants Description: This outcome is assessed in patients waitlisted for a deceased donor kidney transplant and censored at receipt of a deceased donor kidney transplant and at the censoring events included in the main trial analysis (i.e., emigration, trial end date [December 31, 2021], death, evidence of recovered kidney function, or on the date a recorded contraindication to transplant occurs [with the exception of age >75]). 
Changed from: 4.1 years Changed to: 4.17 years
 
Removed:
 
 • Rate of living kidney donor transplants assessed in patients waitlisted for a deceased donor kidney transplant 	
No change was made to these outcomes. We are just providing more clarification on the censoring events.
 
No change was made to the time frame. We simply are providing a more precise time frame and this precise time frame aligns exactly with our published statistical analysis plan.
 
This measure was listed in the protocol but was not analyzed because there was concern that the measure would not provide meaningful information.

Balancing Measures	August 7, 2020	
Added: Balancing Measures
 
 • Proportion of patient referrals to a transplant centre where the referral was declined. 	
We added balancing measures to track whether our multi-component quality improvement intervention, which was designed to improve access to transplant, did not inadvertently introduce problems in other

Revision	Date of Revision	Details of Revision	Rationale
	March 9, 2023	
 • Proportion of patient referrals to a transplant centre where the referral information was incomplete (e.g. missing diagnostics and/or other required patient information). • Proportion of patient referrals to a transplant centre where the referral was deferred. • Proportion of patient referrals to a transplant centre where the referral was accepted. • Proportion of patients referred to a transplant centre who were not waitlisted or transplanted within 1-year of referral. • Average time from patient referral to transplant centre to consulting with a transplant nephrologist (restricted to patients who had a referral that was accepted). • Average time from referral to transplant centre to being waitlisted (restricted to patients who were waitlisted). • Average time from consulting with a transplant nephrologist to being waitlisted (restricted to patients who were waitlisted). • Average time from referral to living kidney donor transplantation. • The proportion of living donor candidates who complete all the following: a nephrology consultation, a surgeon consultation, and a computed tomography angiogram. • Average time from completing the health history questionnaire to the computed tomography angiogram. • Average time from completing the health history questionnaire to donor nephrectomy. • Average time from nephrologist consultation to donor nephrectomy. 
Removed:
 
 • Proportion of patient referrals to a transplant centre where the referral information was incomplete. • Average time from patient referral to transplant centre to consulting with a transplant nephrologist (this measure could also be restricted to patients who received a living kidney donor transplant during the trial period). 	
aspects of care. Further details on balancing measures are described in our published trial protocol.
 
These measures were listed in the protocol but were not analyzed because either the data were of insufficient quality or there was concern that the measure would not provide meaningful information. The published trial protocol indicated some of the balancing measures would be reported during the trial period, while others would be assessed as a change from historical norms pre-dating the trial. For reasons

Revision	Date of Revision	Details of Revision	Rationale
		
 • Average time from consulting with a transplant nephrologist to being waitlisted (this measure could also be restricted to patients who received a living kidney donor transplant during the trial period). • Average time from referral to transplant centre to being waitlisted for patients who received a living kidney donor transplant during the trial period. • The proportion of living donor candidates who complete all the following: a nephrology consultation, a surgeon consultation, and a computed tomography angiogram. • Average time from completing the health history questionnaire to the computed tomography angiogram, restricted to those who ultimately received a living kidney transplant during the trial. • Average time from nephrologist consultation to donor nephrectomy. 	of time, cost, and feasibility we focused on reporting these measures by group only during the trial period.
Statistical Significance	December 5, 2019	
Added: To avoid type I errors due to multiple comparisons, we will use the fixed-sequence procedure, a stepwise multiple-testing procedure where two-sided hypothesis tests for superiority will be performed at the 0.05 significance level in a pre-specified order. We will test the primary outcome first. This will be followed by the five secondary outcomes. Once a hypothesis test is not significant, no further testing will be done. Rather, the analyses of any subsequent secondary outcomes, as well as additional outcomes and other analyses will be reported as point estimates with 95% confidence intervals (without p values); we will indicate that interval widths are not adjusted for multiple testing and therefore inferences drawn may not be reproducible.
	
During the course of our trial newly recommended guidance was published to avoid Type 1 errors due to multiple comparisons.^{1,2,3} To avoid type I errors due to multiple comparisons we will use the fixed-sequence procedure, a stepwise multiple-testing procedure.
 

Revision	Date of Revision	Details of Revision	Rationale
			https://www.nejm.org/author-center/new-manuscripts . Accessed December 4, 2019.
Statistical Power	August 10, 2020	Added: Statistical power calculations for the primary outcome (the number of steps completed towards receiving a kidney transplant) were informed by an analysis of historical administrative healthcare data in Ontario (from November 1, 2016 to October 31, 2017). We estimate a 3.5 year trial should have at least 80% power to detect a rate ratio of 1.5 (this corresponds to patients in the intervention group completing an average of 12 more steps per 100 person-years than patients in the control group [35 steps vs. 23 steps, respectively]; 2-sided $\alpha=0.05$).	At the beginning of the trial the only way we could get power estimates was through conducting a literature review. However, a much more refined way to calculate power is to use historic transplant data that became available to us. Specifically, we could analyze historic data and get event rates which in turn informed our power calculations. See our published trial protocol for further details on our statistical power calculations.
Cohort Selection	August 10, 2020	Added: The primary analysis will be focused on individuals in multi-care kidney clinics (provide care to patients with kidney disease approaching the need for dialysis) or in dialysis programs with no recorded contraindications to kidney transplant in ICES administrative healthcare databases (i.e. patients that are eligible for transplant). Examples of recorded contraindications to transplant include dementia, use of home oxygen, living in a long-term care home, and any comorbidities likely to preclude transplantation. We will also restrict our primary analysis to individuals aged 18 to 80 as few people over age 80 are healthy enough to receive a transplant. Additional details can be found in our published trial protocol. We will also exclude patients from our analysis with invalid or missing data on date of birth or sex, and patients who are not permanent residents of Ontario (<1% will be excluded for a reason of invalid or missing data).	Although the analysis will be restricted to individuals approaching the need for dialysis or patients on dialysis with no recorded contraindications to transplant, the delivery of the intervention is at the CKD program level and all CKD programs in Ontario are included. At the time of the final analysis, pre-specified selection criteria will be applied to restrict the statistical analysis to the patients of interest for trial inclusion.
	June 23, 2022	Changed from: Although older age is not an absolute contraindication to transplant, few people over age 80 are healthy enough to receive a transplant, and transplants in this age group are rare in Ontario; we will therefore exclude those ≥ 80 years of age. Additional exclusion criteria include evidence of any recorded contraindications to transplant including dementia, use of home oxygen (a sign of serious pulmonary disease), living in a long-term care home, and any comorbidities likely to preclude transplantation. Changed to: We found that >97% of patients with one or more of the following characteristics did not receive a transplant in follow-up, and so	We further refined our eligibility criteria based on an analysis we conducted where we compared 80+ baseline characteristics between patients who did and did not receive a kidney transplant during follow-up. ¹ We also further refined our eligibility criteria to exclude individuals receiving conservative renal care; these individuals would not be eligible to receive a kidney transplant as they have opted for conservative care to manage their kidney disease. Conservative renal care is a new variable available in our

Revision	Date of Revision	Details of Revision	Rationale
		
patients with these characteristics will not enter the trial for analysis: an ESKD adapted Charlson comorbidity index score ≥ 7 (a higher score represents greater comorbidity), age >75 years, home oxygen use, dementia, living in a long-term care facility, receiving ≥ 1 physician house call in the past year, or any of the following cancers: bladder, cervical, colorectal, liver, lung, lymphoma, or active multiple myeloma. We have also clarified that receiving conservative renal care will be considered a contraindication to transplant as these patients have decided not to pursue dialysis or transplantation.
 
Added clarification: In our published statistical analysis plan we specified that we are using the 2021 Chronic Kidney Disease—Epidemiology Collaboration Equation, without race, to calculate the estimate glomerular filtration rate.
 
Added clarification: In our published statistical analysis plan we included details on our cohort selection stating, “to ensure stability of kidney function, at least two eGFR or two KFRE measures were required to enter the cohort and these measures had to be separated by at least >90 days but within 365 days.”
	
administrative databases which we did not have access to when we wrote our original protocol.
 
Reference:
 
No change was made. We simply provided clarification on the equation that we will use to calculate the estimated glomerular filtration rate.
 
No changes were made. We are simply providing more details.

Eligibility (as described on ClinicalTrials.gov)	August 10, 2020	
Changed from: Eligibility Criteria: This is a pragmatic cluster randomized controlled trial with eligibility criteria detailed below.
 
Inclusion Criteria:
 
 • All 26 chronic kidney disease (CKD) programs in Ontario. These programs provide care for all chronic dialysis patients in the province. Each CKD program also provides a multi-care kidney clinic for patients with advanced CKD who are progressing to end-stage renal disease. 
Changed to: Eligibility Criteria: This is a pragmatic, two-arm, parallel-group, open-label, registry-based cluster randomized clinical trial with eligibility criteria detailed below.
 
Inclusion Criteria:
 
 • All 26 chronic kidney disease (CKD) programs in Ontario. These programs provide care for all chronic dialysis patients in the province. Each CKD program also provides a multi-care kidney clinic for patients with advanced CKD who are approaching the need for dialysis. 	
No changes were made to the eligibility criteria. We have just provided more detail on the trial design. In the inclusion criteria we also refined the wording to indicate that CKD programs provide a multi-care kidney clinic for patients with advanced CKD who are approaching the need for dialysis (previously we said progressing to end-stage renal disease). The wording now aligns with our published trial protocol.

Revision	Date of Revision	Details of Revision	Rationale
	June 23, 2022	Added clarification: Eligibility Criteria (only bolded word added): This is a pragmatic, two-arm, parallel-group, open-label, registry-based, superiority , cluster randomized clinical trial with eligibility criteria detailed below.	No change was made to the design of the trial, rather we added the term superiority, to align with the wording in our published statistical analysis plan. This trial was always a superiority trial.
Analysis of Trial Outcomes	August 10, 2020	
Analysis of trial outcomes revision 1:
 
Changed from: To determine if a statistically significant difference in the referral rate exists between the multi-component kidney transplant quality improvement program and the standard of care group a Poisson regression model will be used which includes potential confounders but not the intervention status. This method has been found in simulation studies to be robust even when there are a small number of clusters and when the distribution of cluster sizes is skewed. Study data at ICES will be used.
 
Changed to: Study data will be obtained from Ontario's linked administrative healthcare databases at ICES (ices.on.ca). We will account for the study design and covariate-constrained randomization in our analysis. The primary outcome is at the cluster level (the rate of completing steps towards receiving a kidney transplant [per 100 person-years]) and will be compared between groups using a two-stage approach because we have 26 clusters randomized (13 per arm). In the first stage of the model, residuals are obtained from fitting a regression model to the individual level count data adjusting for pre-specified individual-level confounders while ignoring the intervention and clustering effects. In the second stage, the residuals from the first stage are aggregated at the cluster level and used as the outcome to estimate the effect of the intervention. This model fits cluster-level variables and the treatment effect.
	We have refined our analysis based on feedback from our study biostatistician and a review of historic records. The new adopted statistical method was thought to be more appropriate given our updated primary outcome and number of clusters within each arm. The analysis will still be completed at the cluster level and still be done using an intent-to-treat approach. Please refer to our published trial protocol for more details.
	June 23, 2020	
Analysis of trial outcomes revision 2:
 
Changed from the above.
 
Changed to: The primary outcome will be analyzed using a patient-level constrained multi-state model adjusting for the clustering within CKD programs. Bootstrapping at the cluster level will be used to maintain valid inference in the presence of correlated outcomes within CKD programs. We are interested in the global intervention effect for all completed steps towards transplantation. That is, we will be constraining the intervention
	The lead trial statistician, without knowledge of the trial results, considered different approaches as it pertained to statistical power and changed the statistical approach. For several reasons, we changed to a patient-level analysis with a multistate statistical

Revision	Date of Revision	Details of Revision	Rationale
	August 10, 2020 June 23, 2022 August 10, 2020	
effect to be the same for each state transition in our primary analysis. This approach will provide a single estimate of the relative rate (i.e., hazard ratio) of steps completed towards receiving a transplant among patients in CKD programs in the intervention group versus the usual-care group.
 
Changed from: We will censor at death or end of study.
 
Changed to: We will follow patients in our analysis until the end of study, death, receipt of a kidney transplant, or become ineligible for transplant, whichever comes first.
 
Added clarification: A patient's observation time will only stop on the trial end date (December 31, 2021), death, receipt of a kidney transplant, evidence of recovered kidney function, emigration, or on the date a recorded contraindication to transplant occurs (with the exception of age >75 years).
 
Added: A patient's follow-up time will begin on November 1, 2017 or on the earliest date when all eligibility criteria were met up until 3 months before the trial end date (3 months is the expected minimum time to complete early steps towards receiving a kidney transplant). Patients can only enter the analytic cohort once.
	
model, which are fully described in our published statistical analysis plan.
 
We have refined our censoring events to ensure our denominator is capturing the population of interest.
 
In our published protocol we indicated that we would stop following individuals when they become ineligible for transplant. We are also censoring at recovered kidney function as these individuals would not be actively taking steps towards a transplant. We will keep individuals in the trial analysis if they turn aged > 75 years during follow-up given they were 75 years when they entered the trial, and a small proportion of older individuals receive a kidney transplant. As described in our published statistical analysis plan, we will also be censoring at emigration from the province using updated methodology available using our administrative data sources.
 
We provide detail on the timeframe for entering the analytic cohort for analysis.

Additional exploratory analyses	August 10, 2020	
Added: We have added pre-specified subgroup analyses. Specifically, in additional exploratory analyses we will consider subgroup analyses to determine if the intervention improved access to kidney transplant in the following subgroups: receiving maintenance dialysis at the time of trial entry (in-centre or home dialysis), sex (male vs. female), race (white vs.
	
We want to explore the effects of the intervention in different subgroups, with a focus on subgroups that have traditionally experienced lower access to transplant.

Revision	Date of Revision	Details of Revision	Rationale
	June 23, 2022	
other), immigration status, geography (average distance from the patient's place of residence to the transplant centre), income quintile (measured by neighbourhood-level median income), and measures of marginalization (i.e. residential instability, material deprivation, ethnic concentration, and dependency).
 
Changed to: We will not perform subgroup analyses of the intervention effect by race (white vs. other) or immigration status.
 
Added: In addition to the subgroup analyses described in our published protocol, we will also conduct subgroup analyses based on how the patient entered the trial (whether patients were approaching the need for dialysis or receiving maintenance dialysis as well as if patients entered on November 1, 2017 or during the accrual period).
 
Added Clarification: As specified in our protocol, the primary analysis for this trial will not account for pandemic-related changes in transplant activity. However, we will conduct an additional analysis in which patients' follow-up times will be truncated on the date transplant activity was first suspended in Ontario. We are also conducting a concurrent process evaluation using surveys and interviews to understand how the intervention was delivered in each CKD program, and we will ask respondents how the pandemic affected these activities.
	
After consultation with our project partners, we will not perform subgroup analyses by race and immigration status. We do not have access to self-reported race which is considered the gold standard for determining individuals' race and ethnicity. Ethnicity information in the Ontario Renal Reporting System was collected by data leads in each CKD program at the time of patient registration, based on charting by clinical staff who could ask patients to self-identify ethnicity but who were not mandated to do so.
 
We updated our subgroup analyses by including an analysis based on how the patient entered the trial. This was always an intended analysis but was not explicit in the published protocol. This information is detailed in our published statistical analysis plan.
 
Given the challenges of delivering the intervention during the COVID-19 pandemic, we will perform a pre-specified analysis of our primary and secondary outcomes restricting the trial period and follow up from November 1st, 2017 to December 20th, 2019 with follow up to March 16th, 2020. March 16th, 2020 aligns with the suspension of transplant activity in Ontario. It is possible any beneficial effect of the intervention will be more pronounced in the pre-pandemic period.

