Revision	Date of Revision	Details of Revision	Rationale
		
per patient will be considered: (1) patient referred to a transplant center for evaluation, (2) a potential living kidney donor begins their evaluation at a transplant center to donate a kidney to the patient, (3) patient added to the deceased donor transplant wait list, and (4) patient receives a kidney transplant from a living or deceased donor. A patient-level analysis will be used to determine the intervention effect on completed key steps towards receiving a kidney transplant.
 
Time Frame: 4.17 years
	
for the change from a cluster-level analysis to a patient-level analysis.

Secondary Outcome Measures	June 24, 2020	
Changed from:
 
 
1. Kidney transplantation rate (living and deceased donor kidney transplants examined separately and together) Description: The secondary outcome has not been finalized. It will be finalized well before the trial ends and before the analysis of results. The outcome will be published in the peer-reviewed protocol. Time Frame: Two years 
2. Rate of pre-emptive kidney transplantation Description: The secondary outcome has not been finalized. It will be finalized well before the trial ends and before the analysis of results. The outcome will be published in the peer-reviewed protocol. Time Frame: Two years 
3. Rate of kidney transplant waitlisting Description: The secondary outcome has not been finalized. It will be finalized well before the trial ends and before the analysis of results. The outcome will be published in the peer-reviewed protocol. Time Frame: Two years 
4. Average Healthcare Costs Description: The secondary outcome has not been finalized. It will be finalized well before the trial ends and before the analysis of results. The outcome will be published in the peer-reviewed protocol. Time Frame: Two years 	
The average wait time for a deceased donor kidney transplant is approximately five years in Ontario, therefore, we hypothesize that the intervention is likely to have only a small impact on the rate of deceased donor kidney transplants. For this reason, five secondary outcomes have been pre-specified to examine the impact of the intervention on the rate of living kidney donor activity.

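### Several average-time measures cover only patients who reach the event within the trial, so arm differences in them are descriptive and need a censoring-aware companion estimate

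*Combined protocol and SAP*

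**What the plan says.** All references are to rows of the Table of Protocol Updates.

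- **Other pre-specified outcomes.** Outcome 2 is "Average number of months from the date of dialysis initiation (i.e. trial entry) to the date of referral", and "This outcome is assessed in patients receiving maintenance dialysis who were referred to a transplant centre". Outcome 5 (referral to first living donor contact) uses only living donor transplant recipients. For outcome 6 (referral to surgery), "This outcome is assessed in recipients of a living or deceased donor kidney transplant".
- **Balancing Measures.** The averages retained include "Average time from referral to transplant centre to being waitlisted (restricted to patients who were waitlisted", "Average time from referral to living kidney donor transplantation", and time from health history questionnaire to donor nephrectomy. The second and third carry no written restriction, but such times exist only where the operation took place. The March 2023 removals took out other averages, not these three. The balancing measures are reported by group for the trial period. A fixed-horizon measure is also kept: "Proportion of patients referred to a transplant centre who were not waitlisted or transplanted within 1-year of referral".
- **Analysis of Trial Outcomes.** Follow-up starts on November 1, 2017 or at later eligibility, with entry closing 3 months before December 31, 2021. It can end earlier, for example at death, emigration or a new contraindication.
- **June 2022 clarification.** Outcome 1, the deceased donor transplant rate, is defined with "censoring at receipt of a living donor kidney transplant and at the censoring events included in the main trial analysis". No comparable statement appears for outcomes 2, 5 and 6.
- **Statistical Significance.** Outcomes outside the fixed sequence are given as estimates with 95% confidence intervals and no p values. The accompanying caveat concerns multiple testing.

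**The concern.** Each of these averages conditions on an event after randomization that the intervention is meant to influence. Two things follow. First, a time longer than a patient's remaining window cannot be observed, so the average is pulled down and differences between arms shrink. Second, if the intervention brings additional patients to the event, the two averages describe differently selected patients.

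The stake is interpretation. A flat or longer mean time to referral could be taken as no benefit when more patients are referred and nobody waits longer. A small rise in referral-to-waitlist time could be taken as reassurance when listing has slowed by more. The second matters because balancing measures exist to detect unintended harm.

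Outcome 2 also has an unclear origin. It equates dialysis initiation with trial entry, which holds only for patients who start dialysis at entry and not for those already on dialysis on November 1, 2017.

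**Working it through.** **1. The window.** November 1, 2017 to December 31, 2021 is 1,521 days, or 1,522 counting both ends. 1,522/365.25 = 4.167 years, which matches the plan's 4.17. In months this is 50.0. Entry closing 91 days before the end gives a shortest window of 3.0 months.

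**2. Formula.** For event-time density f, distribution function F and individual window w,

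observed mean = E[∫₀ʷ t f(t) dt] / E[F(w)],

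with the expectation over entry dates. If f, entry and exits are the same in both arms, the two means are equal.

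**3. Inputs.** The rate ratio of 1.5 is from the Statistical Power row. The documents give no step-specific timings, so everything else is assumed: exponential times, half the patients present on day 0, and the rest entering uniformly until 91 days before the end.

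**4. Proportional speed-up, outcome 2.** The true fall in mean is 1 − 1/1.5 = 33%.
- Constant referral hazard 0.10/year: observed mean 20.5 to 19.7 months (−4%), while the share referred rises from 27% to 37%. Over hazards of 0.05 to 0.40/year the observed fall is 2% to 15%.
- Only 30% ever referred, mean 12 months: 10.0 to 7.3 (−28%). With mean 6 months: 5.6 to 3.9 (−32%). With mean 24 months: 14.8 to 12.1 (−18%).
- Sensitivity: with 30% or 70% present on day 0, the 0.10/year case reads 18.9 to 18.2 or 21.8 to 20.9. A competing death rate of 0.10/year gives 18.9 to 18.2.

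The direction is always toward no difference. The loss runs from almost none to nearly all of the effect.

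**5. Slowing, referral to wait list.** The true mean is lengthened by one third, with referral hazard 0.10/year in control and 0.15/year in intervention (simulation).

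| True mean, months | Observed mean, months | Share of delay visible |
|---|---|---|
| 6 to 8 | 5.1 to 6.4 | about 65% |
| 12 to 16 | 8.3 to 9.7 | about 36% |
| 24 to 32 | 11.3 to 12.5 | about 15% |

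**6. Selection only, outcome 2.** In control, 30% are ever referred, with mean 12 months. In intervention the same 30% keep the same timing and a further 10% are newly referred. With half present on day 0, (E[F(w)], E[∫t f]) is (0.895, 8.98) for mean 12 months, (0.744, 11.01) for 24 and (0.618, 10.49) for 36.
- Control: 8.98/0.895 = 10.0 months.
- Added patients averaging 12 months: the mean stays at 10.0.
- Averaging 24 months: (0.3×8.98 + 0.1×11.01)/(0.3×0.895 + 0.1×0.744) = 3.795/0.343 = 11.1.
- Averaging 36 months: (0.3×8.98 + 0.1×10.49)/(0.3×0.895 + 0.1×0.618) = 3.743/0.330 = 11.3.

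The 36-month cumulative incidence of referral is 0.3×(1 − e⁻³) = 28.5% in control. It rises to 38.0%, 36.3% and 34.8% in the three cases, so it shows the benefit that the mean hides or reverses. With no patients present on day 0, the control mean is 8.6 and the last two cases read 9.3 and 9.4.

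**7. Outcome 6, deceased donor part.** The Secondary Outcome Measures row says "The average wait time for a deceased donor kidney transplant is approximately five years in Ontario". If that clock ran from referral, 43% to 57% of waits would exceed 50 months (gamma shape 1 to 4, mean 60). In the exponential case, with everyone referred on day 0, the observed mean would be 60 − 50×0.4346/0.5654 = 21.6 months. With steady inflow and all pre-trial referrals counted, the observed mean returns to 60. The result therefore depends on two facts that are not given.

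**8. One-year proportion.** Referrals in the final year, 365/1,522 = 24% of trial time, lack a full year of follow-up. If those not yet listed were counted as not listed, a true proportion p would read 0.76p + 0.24(1 − p)/(−ln p). That turns 40%, 60% and 80% into 46%, 64% and 82%. The documents do not state that counting rule.

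Outcome 5 and the questionnaire-to-nephrectomy average were not quantified.

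**The case against.** The measures are exploratory or balancing, their restrictions are mostly stated openly, and they have no p values. Nothing says that an arm difference will be presented as benefit or harm. The text is a log of changes that refers to a published protocol and SAP for detail. Neither is reproduced here, so silence about censoring does not prove that no method exists. The one-year proportion among all referred patients already guards against unnoticed slowing of listing. All of this stands, and it sets the priority low. It does not remove the point, because the definitions themselves limit the averages to patients with the event, and the no-p-value rule still attaches confidence intervals.

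A reader might infer more than the documents support:
- *That the direction of distortion is always unknown.* It is not. With no effect there is none, and a proportional change is attenuated. A reversal needs selection such as in step 6, where the 10% of slower added patients is an assumption.
- *That outcome 6 must be heavily truncated because five years exceeds 4.17.* The start of the five-year clock is not stated, outcome 6 pools living and deceased donors, and the truncation vanishes if all pre-trial referrals count.
- *That the one-year proportion is biased.* That rests on an unstated counting rule. Even under it, a 20-point gap still reads about 18 (64 − 46, 82 − 64).

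**Conclusion.** The point holds as one of interpretation, at low priority. Outcomes 2, 5 and 6 and the three retained balancing averages are means conditional on a post-randomization event within windows of about 3 to 50 months. They cannot by themselves be read as intervention effects. Under the assumed timings, between about 15% and 65% of a one-third slowing in listing is visible, and mean time to referral can rise by about 1.1 to 1.3 months (0.7 to 0.8 with nobody present on day 0) although no patient is slower. These are illustrations. The documents give no step-specific timings, so the actual size cannot be determined. The multi-state primary analysis, the five secondary outcomes and the censored deceased donor rate are unaffected.

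**What to change.** - **Outcome 2.** Add cumulative incidence, or restricted mean time, of referral from trial entry in all eligible dialysis patients not yet referred. Treat death as a competing event, apply the plan's other censoring events, and take intervals from the cluster bootstrap already planned. State one origin and say how patients already on dialysis on November 1, 2017 are handled.
- **Referral to wait list and referral to transplant.** Add censoring-aware estimates in all patients referred during the trial, with clustered intervals. Say how pre-trial referrals are treated, and note that conditioning on referral remains.
- **One-year proportion.** Limit it to referrals with a full year of potential follow-up, that is, made by December 31, 2020.
- **Event-only means.** Keep them, including outcome 5 and questionnaire-to-nephrectomy, labelled as descriptive summaries. Secondary outcome 2 already covers time to donor evaluation.

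The cost is modest: standard survival code on data already linked, and a summary less simple than average months. The SAP is published and the log runs to August 10, 2023, so added analyses must be labelled post hoc. If none is done, the minimum is one sentence stating that these means are descriptive and not intervention effects.
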